**SAE reports and any other relevant safety information are to be forwarded to the Merck Global Safety [contact]**

A copy of all 15 Day Reports and Annual Progress Reports is submitted as required by FDA, European Union (EU), Pharmaceutical and Medical Devices agency (PMDA) or other local regulators. Investigators will cross reference this submission according to local regulations to the Merck Investigational Compound Number (IND, CSA, etc.) at the time of submission. Additionally investigators will submit a copy of these reports to Merck & Co., Inc. (Attn: Worldwide Product Safety; [contact]) at the time of submission to FDA.

All subjects with serious adverse events must be followed up for outcome.

#### **7.2.3.2 Events of Clinical Interest**

Selected non-serious and serious adverse events are also known as Events of Clinical Interest (ECI). ECIs identified from the date of first dose through 90 days following cessation of treatment, or 30 days after the initiation of a new anticancer therapy, whichever is earlier, must be recorded as such on the Adverse Event case report forms/worksheets and reported within 24 hours to the Sponsor and within 2 working days to Merck Global Safety (Attn: Worldwide Product Safety; [contact]) regardless of attribution to study treatment, consistent with standard SAE reporting guidelines. Events of clinical interest for this trial include:

1. An overdose of Merck product, as defined in Section 7.2.1 - Definition of an Overdose for This Protocol and Reporting of Overdose to the Sponsor, that is not associated with clinical symptoms or abnormal laboratory results.
2. An elevated AST or ALT lab value that is greater than or equal to 3X the upper limit of normal and an elevated total bilirubin lab value that is greater than or equal to 2X the upper limit of normal and, at the same time, an alkaline phosphatase lab value that is less than 2X the upper limit of normal, as determined by way of protocol-specified laboratory testing or unscheduled laboratory testing.\*

**\*Note:** These criteria are based upon available regulatory guidance documents. The purpose of the criteria is to specify a threshold of abnormal hepatic tests that may require an additional evaluation for an underlying etiology. The trial site guidance for assessment and follow up of these criteria can be found in the Investigator Trial File Binder (or equivalent).

1. Additional adverse events:

Subjects should be assessed for possible ECIs prior to each dose. Lab results should be evaluated and subjects should be asked for signs and symptoms suggestive of an immune-related event. Subjects who develop an ECI thought to be immune-related should have additional testing to rule out other etiologic causes. If lab results or symptoms indicate a possible immune-related ECI, then additional testing should be performed to rule out other etiologic causes. If no other cause is found, then it is assumed to be immune-related.

#### **7.2.4 Evaluating Adverse Events**

An investigator who is a qualified physician will evaluate all adverse events according to the NCI Common Terminology for Adverse Events (CTCAE), version 4.0. Any adverse event which changes CTCAE grade over the course of a given episode will have each change of grade recorded on the adverse event case report forms/worksheets.

All adverse events regardless of CTCAE grade must also be evaluated for seriousness.

Table 6 Evaluating Adverse Events

An investigator who is a qualified physician, will evaluate all adverse events as to:

V4.0 CTCAE Grading	Grade 1	Mild; asymptomatic or mild symptoms; clinical or diagnostic observations only; intervention not indicated.
	Grade 2	Moderate; minimal, local or noninvasive intervention indicated; limiting age-appropriate instrumental ADL.
	Grade 3	Severe or medically significant but not immediately life-threatening; hospitalization or prolongation or hospitalization indicated; disabling; limiting self-care ADL.
	Grade 4	Life threatening consequences; urgent intervention indicated.
	Grade 5	Death related to AE
Seriousness	A serious adverse event is any adverse event occurring at any dose or during any use of Merck product that:	
	† Results in death ; or	
	† Is life threatening ; or places the subject, in the view of the investigator, at immediate risk of death from the event as it occurred (Note: This does not include an adverse event that, had it occurred in a more severe form, might have caused death.); or	
	† Results in a persistent or significant disability/incapacity (substantial disruption of one's ability to conduct normal life functions); or	
	† Results in or prolongs an existing inpatient hospitalization (hospitalization is defined as an inpatient admission, regardless of length of stay, even if the hospitalization is a precautionary measure for continued observation. (Note: Hospitalization [including hospitalization for an elective procedure] for a preexisting condition which has not worsened does not constitute a serious adverse event.); or	
	† Is a congenital anomaly/birth defect (in offspring of subject taking the product regardless of time to diagnosis); or	
	Is a new cancer ; (that is not a condition of the study) or	
	Is an overdose (whether accidental or intentional). Any adverse event associated with an overdose is considered a serious adverse event. An overdose that is not associated with an adverse event is considered a non-serious event of clinical interest and must be reported within 24 hours.	

Other important medical events that may not result in death, not be life threatening, or not require hospitalization may be considered a serious adverse event when, based upon appropriate medical judgment, the event may jeopardize the subject and may require medical or surgical intervention to prevent one of the outcomes listed previously (designated above by a †).
							
Duration	Record the start and stop dates of the adverse event. If less than 1 day, indicate the appropriate length of time and units						
Action taken	Did the adverse event cause the Merck product to be discontinued?						
Relationship to test drug	
Did the Merck product cause the adverse event? The determination of the likelihood that the Merck product caused the adverse event will be provided by an investigator who is a qualified physician. The investigator's signed/dated initials on the source document or worksheet that supports the causality noted on the AE form, ensures that a medically qualified assessment of causality was done. This initialed document must be retained for the required regulatory time frame. The criteria below are intended as reference guidelines to assist the investigator in assessing the likelihood of a relationship between the test drug and the adverse event based upon the available information.
 
The following components are to be used to assess the relationship between the Merck product and the AE; the greater the correlation with the components and their respective elements (in number and/or intensity), the more likely the Merck product caused the adverse event (AE):
 
 
 Exposure	Is there evidence that the subject was actually exposed to the Merck product such as: reliable history, acceptable compliance assessment (pill count, diary, etc.), expected pharmacologic effect, or measurement of drug/metabolite in bodily specimen?	
 
 Time Course	Did the AE follow in a reasonable temporal sequence from administration of the Merck product? Is the time of onset of the AE compatible with a drug-induced effect (applies to trials with investigational medicinal product)?	
 
 Likely Cause	Is the AE not reasonably explained by another etiology such as underlying disease, other drug(s)/vaccine(s), or other host or environmental factors	
 
	Exposure	Is there evidence that the subject was actually exposed to the Merck product such as: reliable history, acceptable compliance assessment (pill count, diary, etc.), expected pharmacologic effect, or measurement of drug/metabolite in bodily specimen?	Time Course	Did the AE follow in a reasonable temporal sequence from administration of the Merck product? Is the time of onset of the AE compatible with a drug-induced effect (applies to trials with investigational medicinal product)?	Likely Cause	Is the AE not reasonably explained by another etiology such as underlying disease, other drug(s)/vaccine(s), or other host or environmental factors
Exposure	Is there evidence that the subject was actually exposed to the Merck product such as: reliable history, acceptable compliance assessment (pill count, diary, etc.), expected pharmacologic effect, or measurement of drug/metabolite in bodily specimen?						
Time Course	Did the AE follow in a reasonable temporal sequence from administration of the Merck product? Is the time of onset of the AE compatible with a drug-induced effect (applies to trials with investigational medicinal product)?						
Likely Cause	Is the AE not reasonably explained by another etiology such as underlying disease, other drug(s)/vaccine(s), or other host or environmental factors						

Relationship to Merck product (continued)	The following components are to be used to assess the relationship between the test drug and the AE: (continued)	
	Dechallenge	
Was the Merck product discontinued or dose/exposure/frequency reduced?  If yes, did the AE resolve or improve?  If yes, this is a positive dechallenge. If no, this is a negative dechallenge.
 
(Note: This criterion is not applicable if: (1) the AE resulted in death or permanent disability; (2) the AE resolved/improved despite continuation of the Merck product; or (3) the trial is a single-dose drug trial); or (4) Merck product(s) is/are only used one time.)

	Rechallenge	
Was the subject re-exposed to the Merck product in this study?  If yes, did the AE recur or worsen?  If yes, this is a positive rechallenge. If no, this is a negative rechallenge.
 
(Note: This criterion is not applicable if: (1) the initial AE resulted in death or permanent disability, or (2) the trial is a single-dose drug trial); or (3) Merck product(s) is/are used only one time).
 
NOTE: IF A RECHALLENGE IS PLANNED FOR AN ADVERSE EVENT WHICH WAS SERIOUS AND WHICH MAY HAVE BEEN CAUSED BY THE MERCK PRODUCT, OR IF REEXPOSURE TO THE MERCK PRODUCT POSES ADDITIONAL POTENTIAL SIGNIFICANT RISK TO THE SUBJECT, THEN THE RECHALLENGE MUST BE APPROVED IN ADVANCE BY THE U.S. CLINICAL MONITOR AS PER DOSE MODIFICATION GUIDELINES IN THE PROTOCOL.

	Consistency with Trial Treatment Profile	Is the clinical/pathological presentation of the AE consistent with previous knowledge regarding the Merck product or drug class pharmacology or toxicology?
The assessment of relationship will be reported on the case report forms /worksheets by an investigator who is a qualified physician according to his/her best clinical judgment, including consideration of the above elements.		
Record one of the following	Use the following scale of criteria as guidance (not all criteria must be present to be indicative of a Merck product relationship).	

Yes, there is a reasonable possibility of Merck product relationship.	There is evidence of exposure to the Merck product. The temporal sequence of the AE onset relative to the administration of the Merck product is reasonable. The AE is more likely explained by the Merck product than by another cause.
--	--

No, there is not a reasonable possibility Merck product relationship	Subject did not receive the Merck product OR temporal sequence of the AE onset relative to administration of the Merck product is not reasonable OR there is another obvious cause of the AE. (Also entered for a subject with overdose without an associated AE.)
---	--

### **7.2.5 Sponsor Responsibility for Reporting Adverse Events**

All Adverse Events will be reported to regulatory authorities, IRB/IECs and investigators in accordance with all applicable global laws and regulations.

## **8.0 STATISTICAL ANALYSIS PLAN**

### **8.1 Statistical Analysis Plan Summary**

#### **8.1.1 Safety Analysis**

The All-Patients-as-Treated (APaT) population will be employed for safety analyses. The safety endpoints are all adverse events graded from 1 to 5. Fisher's exact test will be used to compare the proportion of adverse events among patients treated by Pembrolizumab + radiotherapy in this study with historical patients treated by radiotherapy only and compare patients treated by Pembrolizumab + radiotherapy + Cisplatin in this study with historical patients treated by radiotherapy + Cisplatin. Both the adverse events by grade as well as severe adverse event (SAE; yes/no) will be analyzed. RTOG 9501 data will be used for historical controls using targeted rates of 50% for CRT and 39% for RT. We expect that the addition of Pembrolizumab will not add undue toxicity over standard treatment and therefore, will give insight to the development of future trials.

#### **8.1.2 Efficacy Analysis**

All patients who received  $\geq 1$  dose of Pembrolizumab will serve as the primary analysis population in this study. The primary efficacy endpoint is to estimate the disease-free-survival (DFS) (i.e., time from treatment allocation to documented first relapse) at 1 year and 3 years. Key secondary efficacy endpoints include overall survival (OS) (i.e., time from treatment allocation to death due to any cause) at 1 year and 3 years. After resection, patients will be stratified based on adverse risk features. Kaplan-Meier method will be used to estimate survival rates for DFS and OS at 1 and 3 years. The survival rates will be compared with historical censored data (RTOG 9501: 66% in CRT and 58% in RT) using the log-rank test.

We will use estimates of the 95% CI for RTOG 9501 for DFS at 1 and 3 years (see below obtained from RTOG), in order to compare our results.

Study Group	RTOG 9501	
	RT Intermediate Risk	CRT High Risk
Disease Free Survival 1 year (95%CI)	68.8% (59.4%-78.2%)	65.4% (57.1%-73.6%)
Disease Free Survival 3 year (95%CI)	44.1% (34%-54.2%)	45.5% (36.9%-54.2%)

We would expect that adding Pembrolizumab would increase the DFS above these rates in RTOG 9501 and that our results would not fall outside of the lower bound of the CI above.

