### 8.1.3 Power and Sample Size

Based upon RTOG 9501, we expect that DFS at 1 year and 3 years will be 65.4% and 53.5% respectively for patients with high risk features undergoing CRT. We expect to reach similar DFS in this study. We expect that at least 50% of patients (~40 patients) based on defined inclusion criteria will have high risk disease confirmed at resection (+ECE or + margins). With an expected sample size of at least N=40 in the CRT arm, and adding Pembrolizumab to Cisplatin and radiation, we expect to reach over 80% power to detect an increase of 21% in DFS at year 1 (86% DFS compared to 65% at 1 year) using the one-sample exact test at significance level, alpha=0.025 (one-sided). In comparison, assuming that we will reach a similar 1 year DFS of 68.8% in the radiation alone arm, by adding Pembrolizumab, and assuming N=40, we expect to reach over 80% power to detect an increase of 19% in DFS at 1 year (88% DFS compared to 69% at 1 year). Every effort will be made to ensure that we have 40 patients either reached the DFS endpoints or were followed for at least one year without disease recurrence in both strata.

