### **8.2.4.2 Disease Free Survival**

Kaplan-Meier method will be used to estimate the disease free survival rates at 1, 3 and 5 years among patients treated with combined Pembrolizumab, radiation therapy and +/- Cisplatin. 95% CI of these rates will be provided. These survival rates at 1 year will be estimated and compared with historical data (RTOG 9501: 65.4% in CRT and 68.8% in RT) via the one-sample exact test, point and confidence interval estimation. We will also use the log-rank test and Cox model to compare the DFS between the trial data and the historical data if patient level data obtained from RTOG 9501. An interim analysis will be done throughout study at the PI and statistician discretion.

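### Section 8.1.2 sets the intermediate-risk stratum against the overall RTOG 9501 RT-arm rate (58%), while the rest of the SAP uses the intermediate-risk rate (68.8%)

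*Combined protocol and SAP*

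**What the plan says.** Section 8.1.2 sits under the heading "8.1 Statistical Analysis Plan Summary". It states: "The survival rates will be compared with historical censored data (RTOG 9501: 66% in CRT and 58% in RT) using the log-rank test". The sentence gives no condition, and it attaches no endpoint or year to the two rates, although the sentence before it covers both DFS and OS at 1 and 3 years.

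The next sentence of 8.1.2 turns to other figures: "We will use estimates of the 95% CI for RTOG 9501 for DFS at 1 and 3 years". The table under it has one column for intermediate-risk RT, with 1-year DFS of 68.8% (95% CI 59.4% to 78.2%), and one for high-risk CRT, with 65.4% (57.1% to 73.6%). The section then expects DFS above these rates and that "our results would not fall outside of the lower bound of the CI above".

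The later sections follow the table. Section 8.1.3 powers the RT stratum "assuming that we will reach a similar 1 year DFS of 68.8% in the radiation alone arm". Section 8.2.4.2 says "These survival rates at 1 year will be estimated and compared with historical data (RTOG 9501: 65.4% in CRT and 68.8% in RT"), using the one-sample exact test. It adds a Cox model and a log-rank comparison under a condition: "to compare the DFS between the trial data and the historical data if patient level data obtained from RTOG 9501".

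Section 8.2.4.3 plans a log-rank comparison for OS with no named comparator and puts the patient-level condition only on the Cox model.

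**The concern.** The 58% and 66% match the RTOG 9501 RT and CRT columns of the table in 4.2.3.2, which has no risk breakdown. That they describe the whole arms is an inference from that table, but nothing there suggests otherwise.

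For CRT the mismatch is trivial. For RT it is not. Section 5.3 places every patient with positive margins or extracapsular extension in the high-risk group, so the RT stratum has none. Section 4.1.3 says 59% of RTOG 9501 patients had one or both features. That figure is study-wide, and applying it to the RT arm is again an inference. On that reading, 58% describes a worse-prognosis population than the one it would be compared with.

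The trial has no concurrent control, so the efficacy claim depends on the historical comparator. If patient-level RTOG data arrive and 8.1.2 is followed, the milder case mix of the intermediate-risk stratum could be read as a pembrolizumab benefit. Section 8.2.4.2 does not prevent this, because it does not say which RTOG patients enter the log-rank or Cox comparison.

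**Working it through.** **1. The plan's own power figures.** Inputs from 8.1.3: N=40, one-sided alpha 0.025, one-sample exact test. Take the smallest c with P(X ≥ c | 40, p0) ≤ 0.025.

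- RT, p0 = 0.688, p1 = 0.88: c = 34, size 0.0163, power 80.2%.
- CRT, p0 = 0.654, p1 = 0.86: c = 33, size 0.0141, power 81.1%.

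Both agree with the stated power of over 80%. The sample size therefore rests on 68.8% and 65.4%, not on 58% and 66%.

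**2. Size of the discrepancy.**

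- RT, 1 year: 68.8 − 58 = 10.8 points.
- RT, 3 years: 44.1 (8.1.2 table) − 37 (4.2.3.2 table) = 7.1 points.
- SE of the 68.8% estimate: (78.2 − 59.4)/3.92 = 4.80 points, so 58% lies 10.8/4.80 = 2.25 SE below it and 59.4 − 58 = 1.4 points below the lower limit.
- CRT: 66 − 65.4 = 0.6 points, well inside the CI. The cut-off stays at 33/40 (size 0.0171 at 66%).

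**3. Does case mix plausibly explain the gap?** If 41% of the RT arm (100 − 59) was intermediate risk at 68.8%, the rest must have had 1-year DFS of (0.58 − 0.41 × 0.688)/0.59 = 0.505. For an intermediate share of 30% this is 0.534, and for 50% it is 0.472. A rate near 50% in RT patients with high-risk features would account for the gap.

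**4. Effect on a two-sample log-rank test.** RTOG group sizes are not in the documents, so they are inferred from the CI widths:

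- n = p(1 − p)/((U − L)/3.92)²: 93.3 from the 1-year rate and 92.8 from the 3-year rate, so about 93 intermediate-risk RT patients.
- Whole RT arm: 93.3/0.41 = 228.

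Curves are piecewise exponential through the 1- and 3-year rates, with no dropout and no pembrolizumab effect. The trial curve is 68.8%/44.1% and the whole-arm curve 58%/37%. There were 40,000 simulations per cell, counting Z ≥ 1.96 in favour of the trial. N=30 is added because 8.1.3 expects at least half of the 80 patients to be high risk, so the intermediate stratum may fall short of 40.

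| Comparator | Trial N | Events to 1 year | Events to 3 years |
|---|---|---|---|
| Whole RT arm, n=228 | 40 | 21.4% | 15.1% |
| Whole RT arm, n=228 | 30 | 16.5% | 11.8% |
| Intermediate risk, n=93 | 40 | 2.1% | 2.1% |
| Intermediate risk, n=93 | 30 | 1.9% | 2.0% |

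The 3-year figures are lower because the curves separate only in year 1. The first-year hazard ratio is ln(0.688)/ln(0.58) = 0.69. In years 1 to 3 the yearly hazards are almost equal: ln(0.688/0.441)/2 = 0.222 against ln(0.58/0.37)/2 = 0.225.

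**5. Sensitivity (N=40, whole RT arm).**

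- Arm size 150: 20.9% and 14.8%. Arm size 300: 21.9% and 15.4%.
- No-effect rates at the lower ends of the SAP's CIs (59.4%/34%): 2.8% and 1.0%.
- No-effect rates at the upper ends (78.2%/54.2%): 68% and 60%.

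**6. Illustration only, not a rule in the plan.** Were 58% used as the null of the exact test, the cut-off would fall from 34/40 to 30/40 (size 0.0197 at 58%). A stratum with a true rate of 68.8% would then pass 25.4% of the time instead of 1.6%.

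**The case against.** The best case for leaving the text alone is that 8.1.2 is a summary and its sentence looks like a leftover. The detailed DFS section names the right rates and the exact test, and the power calculation agrees with it. A log-rank test takes no fixed 1-year rate as input, so 58% only labels a dataset. Speaking of censored historical data already implies patient-level records. Harm requires that those records arrive, that the summary is followed, and that the whole RT arm is used. The last is doubtful, since 8.1.2 reports that RTOG supplied risk-group estimates for the comparison.

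Much of this stands, and it limits the consequence to a supplementary comparison. It does not remove the contradiction. No section says that 8.2.4.2 prevails, and 8.2.4.2 leaves the RTOG comparison group undefined, so the rates in 8.1.2 are the only ones the SAP attaches to a log-rank test.

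Three further points are fair. The false-positive figures depend on inferred group sizes and run from 1.0% to 68% across the SAP's own CIs. The lower CI limit in 8.1.2 is an expectation, not a decision rule. And 68.8% is not shown to be a matched rate: the table does not define intermediate risk, and entry under 5.1.2 allows T4 disease or T3 oral cavity disease with any N stage. It is the closer rate and the one the plan adopts elsewhere, which is as much as can be claimed for it.

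**Conclusion.** The concern holds. Section 8.1.2 names a comparator for the RT stratum that conflicts with its own table, with 8.1.3 and with 8.2.4.2, and it drops the condition that 8.2.4.2 puts on the log-rank test. The documented size is 10.8 points at 1 year, with 58% below the CI for the rate used elsewhere. The primary exact test, power and sample size are unaffected.

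If the log-rank comparison were run against the whole RT arm, the chance of a false positive at N=40 would be about 21% (to 1 year) or 15% (to 3 years), instead of about 2%. That assumes the historical intermediate-risk rates are the true no-effect rates, an RT arm of about 228, piecewise-exponential curves and no dropout. If the true rates are at the lower CI limits, there is almost no inflation. The text should be corrected before the analysis.

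**What to change.** In 8.1.2, remove the two rates in brackets and replace the sentence with wording such as:

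> For 1-year DFS, each stratum is tested against the RTOG 9501 rate for its own risk group (high-risk CRT 65.4%; intermediate-risk RT 68.8%) with the one-sample exact test, as set out in 8.2.4.2. If individual RTOG 9501 records become available, DFS is also compared by log-rank test and Cox model, using only RTOG patients of the same risk group and treatment. OS is handled as in 8.2.4.3.

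Then:

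- In 8.2.4.2, add the same risk-group and treatment restriction to the log-rank and Cox sentence.
- In 8.2.4.3, put the log-rank test under the same patient-level condition and restriction.
- In 4.2.3.2, say that the whole-arm table is background and that the analysis rates are those in 8.1.2.
- State how the RTOG intermediate-risk group was defined, so that the restriction can be applied.
- Do not attach the 1-year DFS rates to OS or to 3-year results.

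The cost is wording only: one sentence in 8.1.2, a clause in each of the other three sections, and a short definition. Sample size and power do not change.

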### 8.2.2 Efficacy Endpoints

#### Primary Endpoint

Disease Free Survival (DFS): measured from the time of treatment allocation to the time of discovery of the first evidence after treatment of any tumor (local, regional, metastatic, or second primary) or death from any cause. DFS at 1 and 3 years will be the primary efficacy endpoints.

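### Staying above the lower 95% limit of RTOG 9501 is not evidence of benefit; the plan does not subordinate this benchmark to the exact test at 1 year and sets no other sure comparison at 3 years

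*Combined protocol and SAP*

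**What the plan says.** Section 8.1.2 gives the historical intervals an analytic role: "We will use estimates of the 95% CI for RTOG 9501 for DFS at 1 and 3 years", for the purpose of comparing the trial's results. Its table lists DFS for the RTOG 9501 chemoradiation (CRT) high-risk and radiation (RT) intermediate-risk groups. An expectation in two parts follows. The first is "We would expect that adding Pembrolizumab would increase the DFS above these rates in RTOG 9501". The second is "that our results would not fall outside of the lower bound of the CI above". The same section also names a log-rank test against historical censored data.

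Section 8.1.3 powers the trial on a one-sample exact test of 1-year DFS at one-sided alpha 0.025, with 40 patients in each stratum. Section 8.2.4.2 repeats that test, limited to 1 year: "These survival rates at 1 year will be estimated and compared with historical data". It provides Kaplan-Meier estimates with 95% intervals at 1, 3 and 5 years. Its log-rank and Cox comparison applies only if patient-level RTOG data are obtained.

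Section 8.2.2 states "DFS at 1 and 3 years will be the primary efficacy endpoints". Section 4.2.3.2 instead makes 1-year DFS primary and 3-year DFS secondary. The hypotheses in section 3.1 are that DFS will increase relative to historical data.

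**The concern.** RTOG's lower limit describes the sampling error of RTOG's own estimate. Setting this trial's estimate against it leaves out this trial's error, which at about 40 patients per stratum is large. The limit also lies 8 to 10 points below the rate the trial hopes to exceed, so results worse than RTOG can satisfy it.

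No section says how this benchmark relates to the exact test or which of them settles the conclusion. A report could therefore state correctly that results stayed above the RTOG bound, as the plan expected, for an inactive or moderately harmful regimen. The risk is greatest at 3 years, where the plan offers no test that is certain to be available.

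**Working it through.** **Inputs.** RTOG rates and lower limits come from the table in 8.1.2. N = 40 per stratum, alpha = 0.025 one-sided, and alternatives of 86% (CRT) and 88% (RT) come from 8.1.3. The null rates of 65.4% and 68.8% come from 8.2.4.2. X, the number of patients disease-free at the landmark, is taken as Binomial(40, p).

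**Step 1: the plan's own power.** The cut-off is the smallest r with P(X ≥ r | p0) ≤ 0.025.
- CRT: P(X ≥ 33 | 0.654) = 0.014, while P(X ≥ 32 | 0.654) = 0.034. So r = 33, and power is P(X ≥ 33 | 0.86) = 81.1%.
- RT: P(X ≥ 34 | 0.688) = 0.016, while P(X ≥ 33 | 0.688) = 0.040. So r = 34, and power is P(X ≥ 34 | 0.88) = 80.2%.

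The stated power of over 80% is reproduced in both strata.

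**Step 2: the lower-bound benchmark taken alone.** The smallest passing count is c = 40 × lower limit, rounded up. The pass probability is P(X ≥ c | p), with p equal to the RTOG rate (no effect) or to that rate minus 0.10.

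| Comparison | RTOG rate | Lower limit | 40 × limit | c | No effect | 10 points lower |
|---|---|---|---|---|---|---|
| CRT, 1 year | 65.4% | 57.1% | 22.84 | 23 | 88.7% | 45.9% |
| RT, 1 year | 68.8% | 59.4% | 23.76 | 24 | 91.3% | 50.6% |
| CRT, 3 years | 45.5% | 36.9% | 14.76 | 15 | 88.1% | 45.4% |
| RT, 3 years | 44.1% | 34% | 13.60 | 14 | 90.7% | 51.1% |

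At 1 year the benchmark and the exact test differ by 33 − 23 = 10 patients (CRT) and 34 − 24 = 10 patients (RT) out of 40. A CRT result of 23/40 meets the bound, yet its exact 95% interval is about 41% to 73%.

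**Step 3: adding the first half of the sentence.** If the observed rate must also exceed the RTOG point estimate, the required count is the first whole number above 40 × rate.

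| Comparison | 40 × rate | Count needed | No effect | 10 points lower |
|---|---|---|---|---|
| CRT, 1 year | 26.16 | 27 | 46.2% | 8.2% |
| RT, 1 year | 27.52 | 28 | 51.1% | 9.9% |
| CRT, 3 years | 18.20 | 19 | 46.0% | 7.9% |
| RT, 3 years | 17.64 | 18 | 51.5% | 10.1% |

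This is much stricter than the lower bound, but an inactive regimen still passes about half the time.

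**Step 4: sensitivity.** A normal approximation at N = 40 gives 86–90% (no effect) and 41–51% (10 points lower) for the lower bound. Exact calculations for N = 30 to 50 give 78–94% and 37–56%.

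**Step 5: what is left at 3 years.** The exact test covers 1 year only. The log-rank and Cox comparison in 8.2.4.2 is conditional on patient-level data. The log-rank test in 8.1.2 carries no such condition, but it refers to historical censored data and cites only 1-year rates (66% and 58%). Without patient-level data there remain the trial's own Kaplan-Meier estimate and interval, with no stated rule for setting them against RTOG, and the 8.1.2 benchmark.

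**The case against.** A reader might infer that section 8.1.2 judges the trial by the lower bound, so that an inactive drug succeeds nine times in ten. The documents do not support that reading.

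- The lower-bound words are the second half of an expectation. The first half asks for DFS above the RTOG rates, and a trial below those rates fails it.
- The plan nowhere calls the bound a success criterion, test or decision rule. At 1 year it specifies a powered exact test whose actual error is 1.4% (CRT) and 1.6% (RT).
- The primary DFS objectives in 3.1 are to estimate DFS, and 8.2.4.2 supplies estimates with intervals at 3 years as well. It would be wrong to say that the objectives cannot be answered.
- The 88–91% figures are per comparison. If all four bounds had to hold together, with strata independent and 3-year successes nested within 1-year successes, the chance is about 70% with no effect and 12% with DFS 10 points lower.
- Section 4.2.3.2 calls 3-year DFS secondary, so its standing as primary is itself unsettled.

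All of this stands and limits the point. It does not remove it. Section 8.1.2 does present the RTOG intervals as the yardstick, and nothing makes that yardstick subordinate to the exact test. Applying both halves of the expectation together still gives no error control, and at 3 years no tested alternative is guaranteed.

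**Conclusion.** The point holds as one about an uninformative and unranked benchmark. Meeting a lower limit cannot be read as benefit: taken alone it is met 88–91% of the time with no effect and 45–51% of the time with DFS 10 points lower. Exceeding the RTOG point estimate happens 46–52% of the time with no effect.

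At 1 year the remedy is clarification, because a sound test is already planned. At 3 years the gap is material: the endpoint is primary in 8.2.2, and its only assured comparison with history is this benchmark.

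The figures assume 40 evaluable patients per stratum, no censoring before the landmark, an observed proportion in place of the Kaplan-Meier estimate, a true no-effect rate equal to the RTOG estimate, and the RTOG limits treated as fixed.

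**What to change.** 1. In 8.1.2, delete the lower-bound wording or label it descriptive and not evidence of benefit.
2. State in 8.1.2 and 8.2.4.2 that the one-sample exact test decides 1-year DFS. With N = 40 this means at least 33/40 (CRT) and 34/40 (RT).
3. For 3-year DFS, claim an increase only if the lower limit of the trial's own two-sided 95% interval exceeds the RTOG rate in the 8.1.2 table (45.5% CRT, 44.1% RT). The interval should be Kaplan-Meier based, with its method named in advance. Otherwise report the estimate and interval and state that no increase was shown.
4. Reconcile 8.2.2 with 4.2.3.2 on whether 3-year DFS is primary. Also reconcile the 3-year CRT rate of 53.5% in 8.1.3 with the 45.5% in the 8.1.2 table, since the rule in item 3 depends on it.
5. Note that the trial is not powered for the 3-year comparison. For scale, with complete follow-up and an exact interval at N = 40, both strata would need 25/40: P(X ≥ 25 | 0.455) = 0.023 and P(X ≥ 25 | 0.441) = 0.015, whereas 24/40 gives 0.046 and 0.031.

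The cost is SAP wording, with no added patients or data. The downside is that a favourable-sounding statement becomes harder to make.
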